9. STUDY PROCEDURES

Recruitment and Informed Consent Procedures

Wards: During initial contacts with senior managers in each participating NHS Trust/Health Board we will ask them to suggest up to three wards that meet the inclusion criteria that we may approach to seek agreement to participate. All three wards will take part in the questionnaire survey and one of the three wards will be selected for the more in-depth case study of care planning.

Ward staff: All managers and ward staff involved in care planning or care plan review will receive written and verbal information about the study and be invited to participate in the questionnaire survey. On the ward selected for the in-depth case study, purposive sampling will be employed to invite a selection of staff to participate in interviews. Usual procedures for obtaining informed consent with permission to decline or withdraw will be employed. All participants will be anonymous.

Informal/family carers: Ward staff will be asked to give carer questionnaire packs to carers (family members and friends) visiting service users on the ward. The packs will include an information sheet and a Freepost return envelope. Researchers working on the ward will also approach carers to invite them to participate by either completing the questionnaires, with assistance if required, and/or by taking part in an interview.

Service users: Ward staff will be asked to identify service users nearing discharge that in their view have the capacity to be invited to participate in the study. Staff will make an initial approach to the service user, inviting them to meet with the research assistant (RA) to find out more about the study.

The RA will provide the service user with written and verbal information about the study and invite and respond to any questions. During this process the RA will appraise the capacity of

the service user to understand the information and make an informed decision whether to participate. The service user will be given at least 24 hours to consider their decision and will be encouraged to discuss it with family, friends, advocates or staff if they wish. If a service user lacks the capacity to provide informed consent or declines to participate, the next service user approaching discharge from the ward will be approached to participate.

Service users will be invited to participate in the following ways:

- Complete the pack of questionnaires, with assistance from the RA if required; and/or

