In our study we aim to obtain complete questionnaire survey responses from 300 service users (approx. n =50 per site) 300 inpatient staff (approx. n =50 per site) and 150 informal carers (approx. n =25 per site). By sampling 300 survey responses we are sampling in excess of the sample size suggested for the service users and inpatient staff. In contrast, we anticipate that we will not achieve this sample size for informal carers. This is because not every service user will have a carer therefore analysis for the informal carers will be underpowered (estimated power will be 0.44). The data for the informal carers will be exploratory in preparation for a future larger scale study. We anticipate that with non-response and incompletion of the questionnaires we will need to oversample in order to meet the sample sizes.

Calculations for the sample size for qualitative interviews were based on previous research with similar populations by the co-investigators and others; understanding of the practicalities and time commitments of recruiting and interviewing participants and analysing in-depth qualitative data; and the numbers required to feel confident that the findings would be transferable to other similar settings.

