11. DATA ANALYSIS

Analytical framework

This study involves a range of methods including policy review, narrative synthesis, cross-sectional survey, and semi-structured interview methods. Accordingly several distinct approaches to the analysis of findings will be used.

We will frame our data analysis by drawing on social scientific ideas and on the findings of our Phase 1 evidence and policy review, an approach we have used in previous funded studies e.g. Hannigan (2013). Our concern to explore commonplace practices in inpatient mental health settings is congruent with interactionist interests in social processes and human action (Atkinson & Housley 2003). This perspective also recognises the importance of social structures, so that in any given setting person-to-person negotiations are shaped by features of organisational context (Strauss 1978). The immediate context for frontline practitioners/service users in this study is the inpatient unit, each of which we view as a complex, open system. Each participating ward also sits within a larger, meso-level, NHS Trust/Health Board site, which in turn is located within a national-level system of mental health services. This idea of 'nested systems' is a feature of complexity thinking (Byrne 1998), and informs our plan to generate, analyse and connect data at different (but interlocking) macro/meso/micro 'levels' of organisation.

Our Phase 1 policy and literature review will allow us to compare and contrast the largest-scale (or 'macro-level') systems for mental health care across the two countries, and

consider the degree to which ideas of recovery and personalisation are represented in prevailing frameworks. We will analyse what managers and professionals say, and write, about care planning and coordination across participating sites to make the connections between the 'macro' and the 'meso', and in the first instance we will present a detailed account of our six different local organisational contexts in within-case fashion (Ayres et al 2003). The most important phase of our data analysis will be our exploration of what frontline practitioners, service users and carers say, and write, about how actual, individual (or 'micro')-level care is planned and coordinated. We will establish the day-to-day realities of how care is planned and experienced in inpatient settings and the degree to which processes and actions reflect orientations to recovery and personalisation.

Data management

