Questionnaire returns for each site will be entered, checked and cleaned using SPSSv21. The distribution of questionnaire data (VOICE, RSA, STAR and ES) will be assessed for normality by exploring the data graphically using plots and numerically using statistical methods (Shapiro-Wilk and Kolmogorov-Smirnof tests). Descriptive statistics will be calculated and presented in order to provide an overview of clinically significant findings prior to statistical interpretation. To ascertain any differences between the six sites on the four outcome measures for service users, (VOICE, RSA, STAR and ES) a one-way Multivariate Analysis of Covariance (one-way MANCOVA) will be conducted. Covariates will reveal if there are any external influencing factors in care or if these are result of within-case (site) effects. Potential covariates will be patient demographics (i.e. age, gender, ethnicity, diagnosis, and civil/family/accommodation/employment status), diagnosis (type of severe mental illness), and service use (informal/formal, frequencies of admissions, length of stay/service use) and clinical variables (number of staff on ward number of patients). If statistically significant differences are found subsequent One-way Analysis of Covariance (One-way ANCOVA) will be employed post hoc to ascertain which measures differ between which locations. Correlations will be carried out to identify if there is a relationship between the outcome measures. The type of correlation that will be performed will be informed by hypotheses

derived from the descriptive data and the qualitative data. Selective correlations will be conducted using Multiple Linear Regression. Similarly a one-way MANCOVA will be conducted to analyse staff questionnaires (RSA and STAR) with appropriate post hoc analyses. A one-way ANCOVA will be used to analyse the carer questionnaire (RSA) and if significant differences are found Tukey's post hoc test will be conducted.

Qualitative analysis

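### The site comparison ignores the wards within sites, so ward-to-ward variation can be reported as a site difference well above the nominal 5% rate

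*Protocol*

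**What the plan says.** Section 9 (Recruitment and Informed Consent Procedures, Wards) asks senior managers at each site to "suggest up to three wards that meet the inclusion criteria that we may approach to seek agreement to participate", and then states: "All three wards will take part in the questionnaire survey". With six sites that is up to 18 wards. Sections 8 and 10 aim for about 50 service users, 50 staff and 25 carers per site.

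Section 11 (Analytical framework) treats the ward as a system in its own right and places it in a hierarchy: "Each participating ward also sits within a larger, meso-level, NHS Trust/Health Board site".

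Section 11 (Quantitative analysis) then names the models. For service users: "To ascertain any differences between the six sites on the four outcome measures for service users, (VOICE, RSA, STAR and ES) a one-way Multivariate" (the sentence goes on to specify a MANCOVA). For staff: "Similarly a one-way MANCOVA will be conducted to analyse staff questionnaires (RSA and STAR) with appropriate post hoc analyses". For carers: "A one-way ANCOVA will be used to analyse the carer questionnaire (RSA"). Site is the only factor in all three. Ward appears only indirectly, among the potential covariates, as "clinical variables (number of staff on ward number of patients").

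Section 10 bases the sample size of 276 on six groups, four outcomes, 10 predictors, alpha 0.05, power 0.80 and Pillai's V = 0.10, with no ICC or design effect. It concludes: "By sampling 300 survey responses we are sampling in excess of the sample size suggested for the service users and inpatient staff".

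**The concern.** Respondents on one ward share staff, routines and ward rounds. Section 8 says that VOICE covers involvement in care planning and ward rounds, and that STAR is rated for relationships on the ward. Some correlation within wards is to be expected on the protocol's own account. A one-way model with no ward term takes its error from differences between individuals: 300 − 6 = 294 residual df without covariates, or 284 with ten. To claim that sites differ, the relevant yardstick is how much wards within one site differ. With 18 wards that has 18 − 6 = 12 df.

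The stake is attribution. A significant MANCOVA opens the post hoc ANCOVAs that say which measures differ between which locations. One unusual ward among three could produce such a result and be reported as a feature of the Trust or Health Board. In-depth work takes place on only one ward per site, so it may not reveal the true source. Ward staffing and patient numbers, which take at most 18 distinct values each, would also be tested as if they varied by respondent.

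**Working it through.** **1. The plan's own figures.** They reproduce with the G*Power form for MANOVA special effects and interactions. Inputs from section 10: g = 6 groups, p = 4 outcomes, 10 effect df, V = 0.10.

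- s = min(4, 10) = 4; f² = V/(s − V) = 0.10/3.90 = 0.02564
- df1 = 4 × 10 = 40; df2 = s(N − g + s − p) = 4(N − 6); non-centrality = N × s × f²
- Power is 0.7987 at N = 275 and 0.8008 at N = 276, so 276 is reproduced. At N = 150 it is 0.437, matching the stated 0.44.

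Two things follow. Both figures assume independent respondents. And the tested effect has 10 df, whereas site among six groups has 5; with 5 df the same inputs give N = 209.

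**2. Why the site test is too liberal.** Take one outcome with total variance 1, three wards per site, 50 respondents per site and no site effect.

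- True variance of a site mean: ICC/3 + (1 − ICC)/50
- Variance the planned model assumes: about 1/50 = 0.020

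| ICC (assumed) | True variance | Ratio to 0.020 |
|---|---|---|
| 0.01 | 0.0033 + 0.0198 = 0.0231 | 1.16 |
| 0.02 | 0.0067 + 0.0196 = 0.0263 | 1.31 |
| 0.05 | 0.0167 + 0.0190 = 0.0357 | 1.78 |
| 0.10 | 0.0333 + 0.0180 = 0.0513 | 2.57 |

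The ratio equals the design effect 1 + (50/3 − 1) × ICC. For carers, with 25/3 = 8.3 per ward, 1 + 7.33 × ICC gives 1.07, 1.15, 1.37 and 1.73, so the problem is milder there.

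**3. Rejection rates.** Simulation of the nominal 5% site test with no true site effect, six sites, three wards per site unless stated, and outcomes correlated 0.4 to 0.5. With about 1,500 runs, the simulation error at 20% is √(0.2 × 0.8/1500), about 1 percentage point.

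| Test | ICC 0.01 | 0.02 | 0.05 | 0.10 |
|---|---|---|---|---|
| Service users, 4 outcomes, similar clustering on all | 13% | 22% | 60% | 90% |
| Same, no ward effect on the Empowerment Scale | 10% | 22% | 49% | 84% |
| Same as first row, two ward covariates absorb half the ward variance | 8% | 13% | 31% | 64% |
| Same as first row, two wards per site | 19% | 38% | 83% | 98% |
| Staff, 2 outcomes | 11% | 18% | 42% | 71% |
| One outcome, 50 per site, no covariates (as in a post hoc test) | 9% | 14% | 29% | 52% |
| Carers, 1 outcome, 25 per site | 7% | 9% | 17% | 26% |

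In the second row, repeat runs at ICC 0.02 gave 19% to 22%, so the reduction there is small. At ICC 0 the planned service-user test rejects in about 4% to 5%, as it should. A MANOVA on the 18 ward means rejects in 1.5% to 3.3% at every ICC from 0 to 0.10: it does not exceed 5%, and is somewhat conservative.

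**The case against.** **The wards may be the whole target of inference.** The sites are chosen as contrasting cases and managers suggest the wards. The protocol does not say whether these wards are a sample or all that are eligible. If they are fixed, a difference between site means is real for those wards. That stands, and it changes what the error rate refers to. It does not rescue the stated analysis: the plan attributes differences to sites, and without a ward term it cannot separate a site from one of its wards.

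**The study is exploratory.** True, and the cross-case synthesis in section 11 combines qualitative data with summary statistics, not p-values, so the effect on the main synthesis is limited. Carer data are already declared exploratory and underpowered. But the plan still sets significance tests, a power claim and gated post hoc tests.

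**The ward-level covariates help.** They do, by an unknown amount. Half the ward variance is an assumption, and inflation remains under it.

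**Stronger readings that the documents do not support.** A reader might infer:

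- That every questionnaire asks about the ward. Section 8 describes the Empowerment Scale as the respondent's own sense of empowerment and the RSA as recovery-oriented practice in services. Equal clustering on all outcomes is an assumption.
- That 300 divided by the design effect (228 at ICC 0.02) falls short of the required 276. That is the wrong benchmark: 276 belongs to a 10-df effect, the 5-df site effect needs 209 under independence, and neither figure allows for only 12 error df.
- That all three groups are badly affected at any ICC. For carers the rate is only 7% to 9% at ICC 0.01 to 0.02.

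**Conclusion.** The concern holds. The protocol itself names the model, so this is not a detail left to a statistical analysis plan, and the model conflicts with the protocol's own account of wards nested in sites. For service users and staff, even an ICC of 0.01 roughly doubles the 5% error rate or more, unless the ward covariates absorb much of the ward variance (8% for service users if they absorb half). At 0.05 the planned service-user test would reject in roughly 31% to 60% of studies with no site effect, across the three-ward settings examined. For carers the inflation is mild at low ICC.

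The size is conditional on an ICC that the documents do not give, on how much ward variance the covariates explain, on three wards per site (fewer is worse), and on inference beyond the particular wards. Under a fixed-wards reading the fault is one of attribution, not of error rate. The 0.80 power in section 10 assumes independent respondents and cannot be carried over to a test that respects wards.

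**What to change.** - **Data collection.** Print a ward code on every questionnaire pack. Section 9 makes questionnaires anonymous and section 11 describes returns by site; the protocol nowhere says that ward is recorded. The ward covariates imply that it will be known, but if it is not captured at the start it may not be recoverable.
- **Analysis (section 11).** For all three respondent groups, analyse each outcome in a linear mixed model with site fixed, ward as a random intercept within site, and small-sample df (for example Satterthwaite). Alternatively analyse ward means, with 12 error df if all 18 wards take part. Test ward staffing and patient numbers against between-ward variance.
- **If that is judged too imprecise,** report site differences descriptively, by ward, without significance tests.
- **Sample size (section 10).** State that 276 and 0.80 assume independent respondents. Restate power as a range over assumed ICC values, using the 5 df of the site effect and the ward-level error df.

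The cost is wider intervals, lower stated power (the ward-means MANOVA is conservative) and a code on the packs. No extra participants are needed.

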6. STUDY OBJECTIVES

Aims

The aim of this study is to identify factors that facilitate or hinder recovery-focused personalised care planning and coordination in acute inpatient mental health settings.

This study will complement and build on our study of care planning and coordination in community settings (HS&DR Project 11/2004/12) to provide a whole systems response to the challenges faced in providing collaborative, recovery-focused care planning. We also aim to respond to the CQC (2013) questions of how to embed dignity, recovery and participation in inpatient practice when people are subject to compulsory care and treatment.

As an exploratory study guided by the MRC (2008) Complex Interventions Framework the study will generate empirical data, new theoretical knowledge and greater understanding of the complex relationships between collaborative care planning, recovery and personalisation. It will help identify the key components required and provide an informed rationale for a future evidence-based intervention and evaluation aimed at improving care planning and patient outcomes within and across care settings and likely to be acceptable to service users, families/carers, practitioners and service managers. It will also provide lessons for similar, equally problematic, care planning processes in a range of other health/social care settings (Challis et al 2007).

Objectives

To this end we will investigate care planning and coordination for inpatients in acute mental health settings at and throughout three transition stages recognised as key points where care planning can fail (CCAWI 2010):

Stage1: On admission (from community mental health services and via other routes, e.g. police or accident and emergency)

Stage 2: During inpatient care and treatment

Stage 3: In preparation for and at discharge

This novel study will also recognise the different needs of people admitted and detained under the Mental Health Act 1983 and those admitted informally, given the reported challenges of working in partnership with service users detained against their will for assessment and/or treatment.

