10. SAMPLE SIZE

A total of six NHS trusts in England (n=4) and Wales (n=2) will participate in the study.

Within each trust, a questionnaire survey of acute inpatient staff (n per Trust/Health Board=50; total=300), service users (n=50; total=300) and carers (n=25; total=150) that currently or have recently used acute adult inpatient mental health services will be conducted.

Within each trust/health board, one ward will participate in micro-level data collection. Semi-structured interviews with staff (n per ward=6; total=36), service users (n per ward =6; total=36; to include joint review of care plan) and carers (n per ward=4; total=24) will be conducted. Structured case reviews of care plans will be conducted for service users on each participating ward (n per ward = 10; total = 60). Non-participant observation of care planning processes on inpatient units (n per ward=3; total=18)

Justification of the sample size, and the effect size

For the questionnaire survey, an a priori sample size calculation was conducted using the software package G*Power. The sample size was based on completing a multivariate analysis (MANCOVA) for comparing the interaction of within (Covariates) and between factors (sites). Assumptions are based on six groups (sites), four outcome measures (questionnaires) and 10 potential predictors (i.e. gender, age, ethnicity, and time on CPA etc.). We calculated sample size using α level of 0.05, power of 0.80 (Cohen, 1992) and a small effect size (Pillai's Trace V = 0.10). Given the many potential influences on our outcome measures we anticipate that the magnitude of the observed relationship will be

small. A small effect size was therefore chosen in order to represent the subtleties in relationships of the data. This calculation suggests that a sample size of 276 is required in order to reach power.

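### Staff and patient numbers on the ward are listed as potential covariates in the six-site comparison, and the plan claims more for that adjustment than the model can show

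*Protocol*

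**What the plan says.** Protocol section 11 (Quantitative analysis) gives the purpose of the model: "To ascertain any differences between the six sites on the four outcome measures for service users". It then gives the covariates their role: "Covariates will reveal if there are any external influencing factors in care or if these are result of within-case (site) effects".

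The list that follows is tentative ("Potential covariates will be patient demographics") and mixes levels. Age, gender, ethnicity and diagnosis belong to the patient. So does "service use (informal/formal, frequencies of admissions, length of stay/service use". The last group, "clinical variables (number of staff on ward number of patients", belongs to the ward.

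Section 9 asks each Trust or Health Board to suggest up to three wards and says "All three wards will take part in the questionnaire survey". Section 6 gives the purpose of the whole study: "The aim of this study is to identify factors that facilitate or hinder recovery-focused personalised care planning and coordination". Section 11 (Analytical framework) describes wards as systems nested within Trusts and Health Boards, whose organisational features shape what happens between people.

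**The concern.** An ANCOVA separates a confounder from a group effect only if the covariate is not itself part of how the groups differ. Patient case mix can reasonably be treated as something a site receives. Ward staffing and patient numbers are part of how a site delivers care. If a site scores low because its wards are thinly staffed, that is a site effect. The planned model would credit it to the covariate, and the quoted sentence would call it external. This sits badly with a study whose framework treats organisational context as something to be investigated.

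There is a practical consequence. The follow-up ANCOVAs, which are to show which measures differ between which locations, are run only if the MANCOVA is significant. A site difference absorbed by the ward variables would not reach that step.

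**Working it through.** **1. What adjustment does.** In a model with site and covariate x, the adjusted difference between sites j and k is

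(mean y_j − mean y_k) − b × (mean x_j − mean x_k),

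where b is the within-site slope. If x is staffing, the subtracted term is the part of the site difference that the model ascribes to staffing. The model cannot tell whether that part is external to the site or one of its features. That is a question of meaning, which the covariate term does not answer.

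**2. How much information fixes b.** Six sites with at most three wards each give 6 × 3 = 18 wards. Within sites, 18 − 6 = 12 degrees of freedom remain for a ward variable. A one-way model with site as its only factor has no ward term, so it treats these values as about 300 separate readings.

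**3. The limiting case.** If a ward variable takes one value per site, b cannot be estimated. In a rank check, the design matrix with six site columns had rank 6, and still had rank 6 after two covariates constant within site were added. The two sources then cannot be separated.

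**4. The protocol's own sample-size figure.** Section 10 states: "Assumptions are based on six groups (sites), four outcome measures (questionnaires) and 10 potential predictors", with alpha 0.05, power 0.80 and Pillai V = 0.10.
- s = min(4, 10) = 4; f² = V/(s − V) = 0.10/3.90 = 0.0256.
- df1 = 4 × 10 = 40; df2 = 4 × (276 − 6 − 4 + 4) = 1080; noncentrality = 276 × 4 × 0.02564 = 28.3.
- Power is 0.801 at N = 276 and 0.437 at N = 150. The stated 276 and the stated carer power of 0.44 both reproduce. The point made here does not depend on them.

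**5. Illustrative size by simulation.** One outcome; 6 sites × 3 wards × 17 patients; 1500 runs per setting. Assumed: an effect of 0.25 SD and 30-90% of staffing variance lying between sites. The table shows how often the site test is significant.

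| Site difference arises | Unadjusted | Adjusted for staffing |
|---|---|---|
| wholly through staffing | 59-90% | about 5% |
| half through staffing | 49-58% | 27-32% |
| not through staffing | 94-95% | 83-91% |

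The unadjusted rates ignore ward clustering, so the direction is informative and the levels are not.

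**6. Illustrative size by formula.** For the six-site Pillai test at N = 300: df1 = 4 × 5 = 20, df2 = 4 × (300 − 6 − 4 + 4) = 1176, noncentrality = 300 × 4 × f². Suppose V = 0.10 is the effect before adjustment and the same share q is removed on all four outcomes. If q is a share of the mean differences, f² is multiplied by (1 − q)². If q is a share of the explained effect, f² is multiplied by (1 − q).

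| q | Power, share of mean difference | Power, share of f² |
|---|---|---|
| 0 | 0.947 | 0.947 |
| 25% | 0.686 (f² = 0.0144) | 0.841 (f² = 0.0192) |
| 50% | 0.297 (f² = 0.0064) | 0.618 (f² = 0.0128) |

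The documents give no value for q.

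**The case against.** Four points can be made for the plan.

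- **The covariates are only potential.** A reader might infer that the protocol commits to adjusting the site comparison for staffing and patient numbers. It does not, and a final covariate set is commonly left to the SAP. This stands. What can be faulted is the listing of ward variables among patient covariates and the inference stated for them. No later selection makes that inference valid for a ward variable.
- **Length of stay is not simply a site feature.** It is measured per patient and listed with legal status and admissions. It may reflect severity, where adjustment is reasonable, or local practice, where it is not. This stands. Nor is the line elsewhere perfectly clean, since detention and readmission can also reflect local practice.
- **The loss may be smaller than it looks.** A reader might infer that power falls from 0.95 to 0.69 or 0.30. The documents do not support that as an estimate. The shares are hypothetical. V = 0.10 was set for the MANCOVA and may already be the adjusted effect. The 0.947 baseline uses df1 = 20, whereas the protocol's 276 needs df1 = 40, which gives 0.846 at N = 300. Any precision gained from covariates is ignored.
- **Nothing is hidden outright.** A reader might infer that a staffing effect would be lost to the study. It would instead be reattributed to the covariate, which bears on the study aim. Descriptive statistics precede the model, and section 11 brings questionnaire results together for each site before the cross-case analysis. This limits the harm, but it does not repair the stated inference or the conditional follow-up testing.

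**Conclusion.** The point holds in a limited form. The sentence on what covariates show is not supported by the model for ward-level variables. Using them as covariates can remove real site differences and describe them as external. This follows from the structure alone: wards nested in sites, at most 18 of them, 12 degrees of freedom within sites, and no separation at all for a covariate constant within site.

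The size cannot be fixed from the documents. It ranges from little, if few of the differences run through these variables, to nearly complete masking in the adjusted test if all do. The simulated rates and power figures are illustrations under stated assumptions, not predictions. The correction is worth making because it is cheap and concerns a stated inference, not a missing detail.

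**What to change.** - Make the main six-site comparison adjust for patient case mix only, and name in advance which variables count as case mix.
- Report a second, explanatory model that adds the number of staff, the number of patients and length of stay, with the two ward variables handled at ward level. Show how far each site difference changes from the first model to the second.
- Delete the sentence on what covariates show, or limit it to this two-step comparison. A change in a site difference should be described as the part statistically associated with the added variables, not as external.
- Label any power figures for the effect of adjustment as illustrative.

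The cost is one extra model and a wording change. The downside is that case mix captured only by length of stay remains in the main comparison; the second model shows how much that could matter.
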